5.2.3 Electrical Impedance Tomography (EIT)

Patients will be monitored with Electrical Impedance Tomography (EIT) using the TMT impel Medical system (Sao Paulo, Brazil) (12):

Specifically for this study, the Enlight 18000 system will be used to monitor:

Regional distribution of lung ventilation and perfusion: Relative distribution of ventilation and perfusion in predefined regions of interest. The chest plane will be divided into ventral and dorsal regions, and additionally into four quadrants: Upper right and left lungs, and lower right and left lungs. The relative distribution (percentage) of ventilation (tidal volume) and perfusion (cardiac output) will be measured and compared in each selected region.

Changes in lung aeration (Δ EELZ delta end-expiratory lung volume): Direct measurement of static lung volume related to lung collapse and the effects of positive end-expiratory pressure (PEEP).

Pulmonary arterial pulsatility: After filtering the respiratory component using a high-pass filter, changes in impedance caused by pulmonary arterial pulsatility will be analyzed in each region of interest.

Distribution of pulmonary blood flow: Three perfusion studies by EIT will be conducted at each measurement point. To obtain the distribution of pulmonary perfusion, a small volume of 10 ml of 10% saline solution will be injected into the distal lumen of a central venous catheter in the jugular or subclavian position during a brief 20-second apnea. To induce apnea, ventilator settings will be changed to CPAP while maintaining the same PEEP level. The injected saline solution will be analyzed based on the first-pass kinetics, and the perfusion distribution result will be immediately displayed on the monitor. During EIT acquisition, the external temporary pacemaker will be turned off.

5.2.4 Pulmonary Artery Catheter

For patients monitored with a pulmonary artery catheter during the intraoperative period, the following parameters will be recorded: pulmonary artery pressure (PAP), SvO₂, cardiac output (CO), right ventricular systolic work index (RVSWI), pulmonary vascular resistance index (PVRI), pulmonary pulsatility (PAP), effective pulmonary arterial elastance (effPAE), transpulmonary pressure gradient (TPG), and right ventricular pressure (RVP). Since a relatively low number of patients are expected to be monitored with a pulmonary artery catheter, these derived variables will have only descriptive value.

5.3 Specific Study Interventions

5.3.1 Inhaled Nitric Oxide (iNO)

The iNO administration device will be the So Kinox™ (Air Liquide). This device is one of the best and safest clinical devices for administering inhaled nitric oxide, routinely used in the intensive care unit. It ensures accurate dosing of iNO regardless of inspiratory flow and volume. It continuously and accurately monitors the concentration of nitric oxide in inspired gas and the fractions of inspired oxygen and nitrogen dioxide, a toxic byproduct of nitric oxide. The product technical information is available in the supplementary documentation. iNO will be initiated at a dose of 20 ppm immediately after randomization in the corresponding groups. After 30 minutes, a first assessment will be performed, and the iNO dose can be increased to 40 ppm as long as there is no increase in methemoglobin levels above 2.5% and in case there is no improvement in ventricular function or ventricular-vascular coupling, defined by the presence of any of the following:

- $TAPSE \leq 16$ mm
- $TAPSE/PAPs \leq 0.26$
- $S' \leq 9$ cm·sec⁻¹
- $RVOT-AT \leq 100$ ms

5.3.2 Recruitment Maneuver (RM) and PEEP Individualization

In the group assigned to pulmonary recruitment, the maneuver will be performed as follows:

Change the ventilation mode to pressure-controlled ventilation.

Respiratory rate of 15 cmH₂O, FiO₂ 0.4, Inspiratory pressure of 15 cmH₂O, Increase PEEP from 5 to 20 cmH₂O every 5 breaths (20 seconds each step at a respiratory rate of 15). The last step increases inspiratory pressure from 15 to 20 cmH₂O, maintained for 10 breaths (40 seconds). Immediately after completing the maneuver, the ventilation mode will return to volume-controlled ventilation, and a rapid decremental PEEP titration will be performed. PEEP will be reduced stepwise from 16 cmH₂O in 2 cmH₂O steps (30 seconds at each step) while keeping baseline ventilator settings. The closing pressure will be identified based on maximum compliance (17) and/or EIT (18). After a new short recruitment maneuver, ventilation will continue with baseline settings but with PEEP set to the detected closing pressure level.

Safety criteria: The RM will only be performed if stability conditions described in the inclusion criteria are met. The maneuver will be interrupted if any of the following situations occur during the maneuver:

- Desaturation: SpO₂ ≤ 89%
- Mean arterial pressure < 55 mmHg or a decrease ≥ 30% from baseline
- Arrhythmias (tachyarrhythmias >120 bpm or bradyarrhythmias < 50 bpm)
- If the patient requires a pacemaker, heart rate of 70-90 bpm based on hemodynamic response.

5.3.3 Transesophageal Echocardiography (TEE)

An expert cardiologist will perform TEE at three time points during the investigation in all patients following standard procedures. A Philips CX50 portable device will be used.

5.5 Study Protocol

5.5.1 Patient Admission

Routine and specific study monitoring will be initiated. According to the clinical protocol, baseline ventilation will consist of volume-controlled ventilation with VT 6-8 ml/kg; PEEP 5 cmH₂O; RR 15 bpm; I:E 1:2; FiO₂ 1. The first routine blood gas measurement will be obtained with these parameters. Subsequently, FiO₂ will be reduced to 0.4.

5.5.2 Diagnosis of Atelectasis

The presence of atelectasis will be determined using lung ultrasound:

Lung Ultrasound:

Lung ultrasound will be used to confirm atelectasis. Echographic collapse (consolidation pattern) must be present for the patient to be included in the study. Lung ultrasound will be performed at the posterior axillary line in the subdiaphragmatic region. Echographic collapse will be defined as the presence of a consolidation pattern and absence of "lung sliding" or B-lines at the posterior axillary line in the subdiaphragmatic region (19). Alternatively, atelectasis can be confirmed during transesophageal echocardiography (TEE): Presence of a consolidation pattern with dynamic air bronchogram associated with B-lines in the left lower lobe during medial-lower esophageal position of the probe (20). If no ultrasound-visible collapse is present, the patient will not be randomized and will be labeled as a screened patient. Additionally, an air test will be performed to confirm the functional impact of collapse through the air test.

5.7 Study Groups

After confirming atelectasis using the air test and lung ultrasound, patients will be randomly assigned using block randomization to one of the following three groups:

1) Standard treatment (CONT): Patients will be managed according to routine clinical protocol, standardizing interventions in both participating centers.

2) iNO 20-40 ppm (iNO): iNO at 20 ppm will be initiated immediately after randomization and data collection. The dose will be re-evaluated after the first 30 minutes and may be increased to a maximum of 40 ppm depending on the observed response in ventricular function.

3) iNO 20-40 ppm + Pulmonary Recruitment (iNO-RM)

[figure not shown]

Figure 1: Study protocol

5.7.1 Admission Evaluation

Upon admission, patient monitoring and stability will be checked. After routine arterial and venous blood gas extraction, the air test and lung ultrasound will be performed to determine the presence of atelectasis. If the presence of collapse is confirmed, informed consent will be obtained from the family if it has not been given previously. If affirmative, randomization will be conducted, and impedance belts will be placed.

5.7.2 Protocol Measurement Time Points:

T1: Admission

Baseline measurements will be taken upon arrival in the intensive care unit, once the patient has been monitored, postoperative atelectasis has been confirmed (using lung ultrasound or air test), and the patient is in a stable condition after initial laboratory tests.

T2: Baseline

30 minutes after the first measurement under reference ventilation conditions. Depending on the observed response in right ventricular function, the iNO dose will be adjusted. If no improvement is observed, the iNO dose will be increased to 40 ppm.

T3: Final

30 minutes after applying the specific protocol for each group.

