5.8.1 Sample Size

At the participating hospital (Hospital Universitario de la Princesa), cardiac surgery provides a continuous daily flow of patients (one or two per day) who could potentially become candidates for the study if they meet inclusion criteria and not exclusion criteria. Assuming a 15% improvement in right ventricular function measured by echocardiographic parameters in response to iNO or pulmonary recruitment (9) and a confidence level of 95%, the estimated sample size will be 54 patients, 18 in each group (27 per center). However, due to the lack of

Versión 2: September 1, 2023

sufficient studies analyzing right ventricular response to iNO, RM, or both, the final sample size may be adjusted based on preliminary results from initial pilot patients and study progress.

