5.8.2 Statistical Methods

Variables will undergo descriptive analysis of central tendency measures including mean, median, dispersion, standard deviation, and interquartile range, respectively. Homoscedasticity and normality assumptions will be confirmed using Levene's and Shapiro-Wilk tests, respectively.

Variables with normal distribution and similar variance will be compared using the t-test, and variables with non-normal distribution using the non-parametric Wilcoxon test. Pearson's chi-squared test will be used for categorical variables to compare groups at the three measurement points in the study, and Fisher's exact test when expected frequencies are < 5 .

For the comparison of more than two means with homoscedastic variances and normal distribution, ANOVA with post hoc testing will be conducted. For variables with heteroscedastic variances and/or non-normal distribution, the Kruskal-Wallis post hoc test will be applied. To analyze temporal evolution, a repeated measures ANOVA will be used with the intervention type as the main factor. In case of non-normality, the non-parametric Friedman test will be applied. Statistical significance will be set at $p \leq 0.05$. Statistical analysis will be performed using Stata v.15.

6. Safety and Adverse Events

To ensure safety during the 2-hour duration of the research protocol, the following precautions will be taken:

The inclusion of unstable patients or those who have had significant intraoperative complications leading to instability will be avoided.

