6.1 Use of Inhaled Nitric Oxide (iNO)

1. The use of high and prolonged doses of iNO can be associated with adverse effects such as the formation of methemoglobin and NO₂. Methemoglobin levels above 8-10% can lead to symptoms related to functional anemia, as methemoglobin cannot bind oxygen. NO₂ is a common air pollutant that can be toxic at elevated levels due to the formation of reactive oxidative stress species.

Given the doses used and the duration of use, it is unlikely that elevated levels of both will occur. However, methemoglobin levels will be monitored through two blood gas measurements, one at 30 minutes and another at the end of iNO administration (1 hour). The SoKinox system continuously monitors NO₂ levels in the inspired gas and has safety alarms.

iNO may precipitate or worsen left heart failure in patients with preexisting ventricular dysfunction due to increased left preload. This protocol specifically excludes patients with poor preexisting ventricular function or instability. Cardiac function will be monitored through echocardiography performed at 30 minutes (T2) and immediately after (T3) iNO administration. If there are clear signs of deteriorating left ventricular function (more than 20% drop in LVEF) during the examination compared to the initial function measured upon admission (T1), administration will be stopped.

The following criteria (any of them) will be established for dose reduction or discontinuation of iNO:

- NO₂ levels > 1 ppm
- Methemoglobin fraction > 2.5%
- Variations in inspired oxygen concentration \pm 5% compared to ventilator settings
- Development of left ventricular failure data (drop in LVEF > 20% compared to initial level (T3) in echocardiographic controls.

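### Section 5.7.2 requires the 30-minute iNO increase with no safety condition, at odds with 5.3.1, 5.7 and 6.1; the 6.1 list also gives the wrong LVEF reference time

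*Protocol*

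**What the plan says.** The protocol states the 30-minute dose decision in three places.

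- Section 5.3.1, which describes the intervention: "the iNO dose can be increased to 40 ppm as long as there is no increase in methemoglobin levels above 2.5"%. It also requires that there be no improvement, which it defines by any one of four echocardiographic thresholds (for example TAPSE at or below 16 mm).
- Section 5.7, which describes the groups: the dose "may be increased to a maximum of 40 ppm depending on the observed response in ventricular function".
- Section 5.7.2, which lists the measurement times, under T2: "If no improvement is observed, the iNO dose will be increased to 40 ppm". It cites neither 5.3.1 nor 6.1.

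Section 6.1 then sets the limits on iNO. Any one of four findings calls for cutting or stopping the gas: NO₂ above 1 ppm, methemoglobin above 2.5%, a 5% deviation in inspired oxygen, or an LVEF drop above 20%. On timing, it says "Cardiac function will be monitored through echocardiography performed at 30 minutes (T2) and immediately after (T3) iNO administration" and "methemoglobin levels will be monitored through two blood gas measurements, one at 30 minutes and another at the end of iNO administration (1 hour").

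For LVEF, the paragraph in 6.1 takes admission as the reference: a drop of more than 20% "compared to the initial function measured upon admission (T1), administration will be stopped". The list below it repeats the criterion but labels the initial level T3. Section 5.7.2 defines T3 as the final measurement.

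**The concern.** The same decision, at the same minute and in the same patient, should have one answer. Here the time-point section makes the increase obligatory, while the intervention section makes it optional and bars it above a methemoglobin limit. The time-point section is a natural place for bedside staff to look at T2.

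The timing matters. Under 6.1, the second methemoglobin sample comes at the end of iNO and the second echocardiogram immediately after it. T2 is therefore the only scheduled methemoglobin and LVEF check whose result can still change the dose, and it is where the mandatory wording sits.

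The verb also matters in patients with no safety finding. When there is no improvement, staying at 20 ppm complies with 5.3.1 and 5.7 but departs from 5.7.2. Two centers could apply this differently, and section 7.7 asks the monitors to verify that dosing follows the protocol.

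The T3 label is a separate slip, but it sits in a stopping criterion, which should be usable as printed.

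**Working it through.** No figure in the protocol needs reproducing. The check sets the sections side by side and adds some simple counts.

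**Step 1. Same time point.** Section 5.3.1 places the first assessment 30 minutes after iNO starts. Section 6.1 equates 30 minutes with T2 and takes the first methemoglobin sample then. Section 5.7.2 places the dose change at T2. All three describe one moment.

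**Step 2. What each section directs at T2 for a patient on 20 ppm with no improvement (for example TAPSE ≤ 16 mm).**

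| Additional finding at T2 | 5.3.1 | 5.7 | 5.7.2 | 6.1 |
|---|---|---|---|---|
| None | increase allowed | increase allowed | increase required | no action |
| Methemoglobin > 2.5% | increase not allowed | no safety condition stated | increase required | reduce or stop |
| LVEF drop > 20% from T1, methemoglobin ≤ 2.5% | increase allowed | no safety condition stated | increase required | stop |

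Row 1 differs only in the verb. In row 2, 5.7.2 contradicts both 5.3.1 and 6.1. In row 3, none of the three dosing statements blocks the increase, because methemoglobin is the only safety condition in 5.3.1. Only 6.1 does.

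**Step 3. The LVEF criterion in the 6.1 list, taken as printed.**

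- At T2 the reference LVEF(T3) has not been measured, so the criterion cannot be evaluated.
- At T3 the drop is LVEF(T3) − LVEF(T3) = 0, which never exceeds 20%.
- It can therefore trigger at 0 of the 2 scheduled checks. With T1 as the reference, it can be applied at 2 of 2.

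**Step 4. Size.**

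- Planned enrollment: "the estimated sample size will be 54 patients, 18 in each group (27 per center"). Two of the three groups receive iNO, so 2 × 18 = 36 of 54 patients (67%) face a T2 dose decision. This is a ceiling, not the number in conflict.
- Dose step: 40 / 20 = 2-fold. Time at the higher dose: 60 − 30 = 30 minutes, taking the end of iNO as 1 hour, as in 6.1.
- Patients in rows 2 and 3: the protocol gives no frequency. Section 6.1 considers raised methemoglobin and NO₂ unlikely at these doses and this duration, and says nothing about how often LVEF would fall by more than 20%.

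**The case against.** The strongest reply is that nobody's dosing is really in doubt. Section 5.7.2 is a timetable. The operative rule is in 5.3.1, which alone defines no improvement, so 5.7.2 cannot be applied without it. Section 6 opens with "To ensure safety during the 2-hour duration of the research protocol, the following precautions will be taken", and its LVEF stop has no exception, so a careful reader would let 6.1 prevail. The T3 label is evidently a slip, since the word initial and the preceding paragraph both point to T1. NO₂ is monitored continuously with alarms, and 6.1 says that patients with poor ventricular function or instability are excluded. The 40 ppm dose is itself part of the planned range.

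Most of this stands, and it rules out several stronger readings that a reader might infer:

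- *The escalation in 5.7.2 is unconditional.* It is not. It requires that no improvement be observed; what it lacks is a safety condition.
- *The LVEF safeguard is disabled.* It is not. The T1 paragraph in 6.1 still works.
- *Thirty-six patients are exposed to conflicting instructions on safety.* That figure counts everyone with a dose decision. The safety conflict needs both no improvement and a 6.1 criterion at T2.
- *The permissive verb is the correct one.* The protocol does not settle this. A mandatory increase subject to 6.1 would be equally coherent and would standardize dosing more.

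The reply does not make the texts agree. An abbreviation of 5.3.1 would have kept its verb; replacing *can* with *will* changes the rule. That 6.1 should prevail is an inference, since 5.7.2 does not refer to it.

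**Conclusion.** The concern holds as a minor inconsistency in an operative dosing rule, together with a wrong time label in a stopping criterion. At T2, 5.7.2 requires an increase that 5.3.1 may bar and that 6.1 may turn into a reduction or a stop. The LVEF criterion in the 6.1 list contradicts the paragraph above it and cannot trigger as printed.

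The safety effect is confined to iNO patients who show no improvement and also meet a 6.1 criterion at T2. Their number is unknown and probably small. For them, following 5.7.2 literally would mean twice the dose for about 30 minutes. This assumes that staff read 5.7.2 alone; if they apply 6.1, as they ordinarily would, no patient is wrongly escalated. Sample size, endpoints and analysis are not affected.

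**What to change.** 1. In 5.7.2, and likewise in 5.3.1, make the increase to 40 ppm subject to two conditions: no improvement as defined in 5.3.1, and no 6.1 criterion present. Add that 6.1 applies if any criterion is met. This also closes the LVEF gap in 5.3.1.
2. Use one verb for the increase in 5.3.1, 5.7 and 5.7.2. Permissive and mandatory wording are both workable; the investigators should choose one so that both centers dose alike.
3. In the 6.1 list, change the LVEF reference from T3 to T1.

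The cost is a protocol wording change. LVEF at T2, methemoglobin at 30 minutes, and NO₂ and inspired oxygen from the delivery device are already planned, so no new measurement is needed.

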5.8 Statistical Analysis

Patients will be assigned to intervention groups through block randomization to ensure equitable distribution among the three intervention groups.

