7.7 Monitorin

- Given that only 2 centers (Madrid and Barcelona) are participating in the study, it is planned to have 2 monitors located in each of the respective centers/cities. The monitor cannot, under any circumstances, be part of the investigative team.
- The objectives of study monitoring will be to ensure that:
- The rights and integrity of the subjects are protected.
- Trial data is accurate, complete, and verifiable with source documents.
- The trial is conducted in compliance with the approved protocol, following GCP and current regulations.

Monitoring Plan:

- Given the characteristics of the study, a risk-focused monitoring approach will be implemented. The variables collected in the CRF will be reviewed with special emphasis on safety variables and adverse effects. Verification and validation of the collection of key variables will be performed.
- Three monitoring visits will be scheduled (2 during the study and one final closing visit) during which the following checks/verifications will be conducted:
 - Critical variables to be monitored:
 - Verification of the collection of:
 - I. Informed Consent Verification
 - II. Confirmation of eligibility criteria
 - III. Correct randomization and administration of study drug
 - IV. Verification that identified data as critical variables. Review of source documents
 - V. Review of safety assessments (AEs, SAEs)
 - **Specific verifications to be performed at each visit:**
 - a) Written informed consent was obtained before each subject's participation in the trial.
 - b) The investigator recruits only subjects who meet the selection criteria.
 - c) The approved protocol is being followed correctly.
 - d) The time and storage conditions of iNO are acceptable, and supplies are sufficient during the trial; it is only administered at the doses specified in the protocol.
 - e) Source documents and other trial records are accurate, complete, up-to-date, and properly archived.
 - f) Accuracy and integrity of data entered into the CRF with respect to source documents and other trial-related records.
 - g) All adverse events have been reported appropriately and within the timelines specified in GCPs, the protocol, the Ethics Committee (CEIm), and relevant legal requirements.
 - h) The investigator maintains essential documents (Investigator File).

Versión 2: September 1, 2023

- i) Reporting any protocol deviations and taking necessary actions to prevent recurrence of detected deviations.

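### Stratification by centre is not specified, and no centre term is named in the analysis, although 27 patients are planned at each of two centres

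*Protocol*

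**What the plan says.** Allocation is described in two places. Protocol section 5.7 (Study Groups) says that "patients will be randomly assigned using block randomization to one of the following three groups". Section 5.8 (Statistical Analysis) says "Patients will be assigned to intervention groups through block randomization to ensure equitable distribution among the three intervention groups". Balance across arms is the only purpose given. Neither place mentions centre, the structure of the list or the block size.

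Section 5.8.1 (Sample Size) states that "the estimated sample size will be 54 patients, 18 in each group (27 per center". The monitoring section (7.7) confirms two sites in different cities: "Given that only 2 centers (Madrid and Barcelona) are participating in the study".

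Section 5.8.2 (Statistical Methods) lists two-group tests, ANOVA, Kruskal-Wallis and a repeated-measures ANOVA. Type of intervention is the only between-patient factor it names. Centre does not appear.

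**The concern.** The planned totals fit nine patients per arm in each centre, but nothing in the text secures that split. Blocking on arm balances the arms overall. It balances them within a centre only if each centre has its own list.

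The main outcomes are transoesophageal echo measurements taken at two hospitals in different cities, so some centre difference in level is plausible. If there is one, an uneven centre mix adds noise to the arm comparison. Leaving centre out of the model also leaves its variation in the error term. With 18 patients per arm there is little precision to spare.

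Timing matters too. A centre factor in the model can be settled in a later analysis plan. The structure of the allocation list has to be settled before the first patient is randomized.

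**Working it through.** **Inputs from the protocol.** Total 54, 18 per arm, 27 per centre, effect 15% (section 5.8.1); significance level 0.05 (section 5.8.2). SD, power and sidedness are not given, nor is any centre effect.

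**The plan's own figure.** The counts agree: 3 × 18 = 2 × 27 = 54, and 54 / (3 × 2) = 9 per arm per centre. The 54 itself cannot be reproduced without an SD and a power. Working backwards at two-sided 0.05 and 80% power (assumed), 18 per arm implies SD = 15 / [(1.96 + 0.842) × √(2/18)] ≈ 16.1%. That value only sets the scale below; the imbalance results do not use it.

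**Imbalance if one common list were used.** Treat the 27 patients of one centre as a random half of the 54 allocations.
- Exact 9/9/9: C(18,9)³ / C(54,27) = 0.059, about 6%.
- Variance of one arm's count in a centre: 27 × (1/3) × (2/3) × (27/53) = 3.06, so the SD is 1.75 around a mean of 9.
- Variance of the difference between two given arms: 3 × 3.06 = 9.17, SD 3.03. The mean absolute difference is 2.4 patients. The difference is 4 or more in about 25% of trials and 6 or more in about 7%.
- Largest minus smallest of the three arms: 3 or more in about 65%, 4 or more in about 46%, 6 or more in about 15%.

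Simulation with common-list block sizes of 3, 6, 9, 18 and 54 (20,000 runs each) gives almost the same figures, so block size hardly matters.

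**With a list per centre.** Blocks of 3 or 9 give exactly 9/9/9 in each centre. Blocks of 6, which do not divide 27, leave a spread of at most 2.

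**Shift in the arm contrast.** Shift = (difference in count / 18) × centre difference. With an assumed centre difference of 0.5 SD:
- average imbalance: 2.4 / 18 × 0.5 = 0.07 SD;
- tail imbalance (12 against 6): 6 / 18 × 0.5 = 0.17 SD.

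**Added noise.** The standard error of the contrast over repeated allocations, in SD units, is √(2/18 + 9.17/18² × d²) for a centre difference d. This is 0.333 at d = 0, 0.344 at d = 0.5 and 0.373 at d = 1.

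**Power for one pair of arms at a single time point.** Simulation, 4,000 runs per allocation method and shift, true effect 15%, SD 16.06%. The t-test has about 78% power with no centre difference; the 80% comes from the normal approximation.

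| Allocation and model | Shift 0.5 SD | Shift 1 SD |
|---|---|---|
| Common list, no centre term | 74% | 69% |
| Stratified, no centre term | 75% | 69% |
| Common list, centre term | 76% | 76% |
| Stratified, centre term | 78% | 78% |

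Simulation error is about 0.7 percentage points (one standard error), so differences of one point mean nothing.

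**Type I error.** Common list without a centre term: 4.8% and 4.9%. Stratified without a centre term: 4.5% at 0.5 SD and 2.7% at 1 SD, which is conservative. Stratified with a centre term: 5.2% and 5.1%.

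**The case against.** **The text is silent.** A reader might infer that one common list will be used and centre deliberately ignored. The protocol does not say so. Two lists of 9/9/9 would produce exactly the stated totals, so the imbalance figures are conditional on a common list. This stands, and it is why the point is that stratification is not specified. Silence still leaves a common list open as a valid reading.

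**No centre effect is documented.** A reader might also infer that results depend on each centre's echo operator. The number of operators is not stated. The protocol fixes the echo recommendations, the echo device, the ventilator and the baseline ventilation, and it asks that interventions be standardized across centres. The 0.5 and 1 SD shifts are therefore assumptions.

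**Repeated measurements protect the comparison.** Each patient has echo at three time points, and a constant centre offset cancels in change from T1. This stands for such analyses. But section 5.8.2 also allows plain group comparisons at a time point and does not make change from T1 the primary comparison.

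**The imbalance could be read as bias.** It is not. It is random, its average is zero and type I error holds. The 12-against-6 split is a tail case: about 7% of trials for a given pair of arms differ by 6 or more.

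**Stratifying alone gains little, and the centre term is analysis-plan material.** The first half is right: the table shows nearly all the gain coming from the model. The second half is fair for the model term, but not for the list, which a later analysis plan cannot change once allocation has started.

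**Conclusion.** The point holds as an omission. The protocol asks for block randomization to balance the arms, plans 27 patients in each of two centres, and names centre neither as a stratification factor nor as a model term.

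The size is modest. The loss from ignoring centre is about 4 points of power at an assumed 0.5 SD centre difference (78% to 74%) and about 9 points at 1 SD (78% to 69%). These figures assume a common list, a single-time-point comparison and an SD chosen to give about 80% power. If centres do not differ, or if the analysis uses change from T1 and the centre difference is constant, there is essentially no loss.

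The documents do not support saying that the allocation is wrong, that the result would be biased, or that 54 patients are too few. This is a free improvement of minor to moderate weight.

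**What to change.** Make two changes together.

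1. In sections 5.7 and 5.8, state that randomization is stratified by centre, with a separate concealed block list for each centre and undisclosed, varied block sizes, aiming at about 9 per arm per centre. Varied sizes matter because no blinding of treatment is described and short fixed blocks can be guessed. Block sizes that add up to 27, in random order (for example 3 + 6 + 9 + 9), give exactly 9 per arm if a centre stops at 27. If recruitment departs from 27, or the total is adjusted as section 5.8.1 allows, the split will be close rather than exact.
2. In section 5.8.2, include centre as a fixed factor in the between-group models.

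Stratifying without the centre term recovers almost no power and makes the test conservative. The centre term without stratification gets most of the gain but leaves the within-centre split to chance.

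The cost is a few sentences, a second list and one degree of freedom in the model, with no extra patients. If allocation has already begun, the protocol should state which list structure is in use; the centre term can still be added before the data are analysed.
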